8.10. Health Economics

Health economics/medical resource utilization and health economics parameters are not evaluated in this study.

9. STATISTICAL CONSIDERATIONS

Detailed methodology for summary and statistical analyses of the data collected in this study is outlined here and further detailed in a SAP, which will be maintained by the sponsor. The SAP may modify what is outlined in the protocol where appropriate; however, any major modifications of the primary endpoint definitions or their analyses will also be reflected in a protocol amendment.

9.1. Estimands and Statistical Hypotheses

9.1.1. Estimands

For the primary objective of the study, the primary estimand (Estimand 1.1) will use a composite estimand strategy, in participants with biopsy-confirmed NASH and fibrosis, as assessed by the sponsor-identified central pathologist(s), to estimate the treatment effect of DGAT2i doses administered alone and coadministration of DGAT2i + ACCi relative to placebo, and coadministration of DGAT2i + ACCi, relative to DGAT2i alone, in terms of the proportion of 'clinical responders', defined as participants achieving centrally adjudicated: resolution of NASH without worsening of fibrosis or improvement in fibrosis by ≥1 stage without worsening of NASH, or both, at Week 48 and treating all cases of withdrawal from treatment for lack of efficacy or toleration as non-responders. All treatment effect contrasts

will be obtained through fitting the Bayesian dose-response and/or exposure-response models with a logit transformation, or logistic regression models.

A secondary estimand to assess the primary objective will be:

• Estimand 1.2: Using a hypothetical estimand strategy, in participants with biopsyconfirmed NASH and fibrosis, as assessed by the sponsor-identified central pathologist(s), estimate the treatment effect of DGAT2i doses administered alone and coadministration of DGAT2i + ACCi relative to placebo, and coadministration of DGAT2i + ACCi, relative to DGAT2i alone, in terms of estimating the proportion of 'clinical responders', defined as participants achieving centrally adjudicated: resolution of NASH without worsening of fibrosis or improvement in fibrosis by ≥1 stage without worsening of NASH, or both, at Week 48, assuming all participants had remained in the trial and received treatment as planned without withdrawal up to 48 Weeks. Endpoint data collected after treatment withdrawal will be censored. All treatment effect contrasts will be obtained through fitting the Bayesian dose-response and/or exposure-response models with a logit transformation, or logistic regression models.

Secondary estimands to assess secondary objectives will be:

- Estimand 2.1: Using a composite estimand strategy, in participants with biopsy-confirmed NASH and fibrosis, as assessed by the sponsor-identified central pathologist(s), estimate the treatment effect of DGAT2i doses administrated alone and coadministration of DGAT2i + ACCi relative to placebo, and coadministration of DGAT2i + ACCi, relative to DGAT2i alone, in terms of the proportion of 'clinical responders', defined as participants achieving centrally adjudicated resolution of NASH without worsening of fibrosis, at Week 48 and treating all cases of withdrawal from treatment for lack of efficacy or toleration as non-responders. All treatment effect contrasts will be obtained through fitting the Bayesian dose-response and/or exposure-response models with a logit transformation, or logistic regression models.
- Estimand 2.2: Using a composite estimand strategy, in participants with biopsy-confirmed NASH and fibrosis, as assessed by the sponsor-identified central pathologist(s), estimate the treatment effect of DGAT2i doses administered alone and coadministration of DGAT2i + ACCi relative to placebo, and coadministration of DGAT2i + ACCi, relative to DGAT2i alone, in terms of the proportion of 'clinical responders', defined as participants achieving centrally adjudicated improvement in fibrosis by ≥1 stage without worsening of NASH, at Week 48 and treating all cases of withdrawal from treatment for lack of efficacy or toleration as non-responders. All treatment effect contrasts will be obtained through fitting the Bayesian dose-response and/or exposure-response models with a logit transformation, or logistic regression models.
- Estimand 2.3: Using a composite estimand strategy, in participants with biopsyconfirmed NASH and fibrosis, as assessed by the sponsor-identified central pathologist(s), estimate the treatment effect of DGAT2i doses administered alone and

coadministration of DGAT2i + ACCi relative to placebo, and coadministration of DGAT2i + ACCi, relative to DGAT2i alone, in terms of the proportion of 'clinical responders', defined as participants achieving centrally adjudicated improvement in fibrosis by ≥2 stages without worsening of NASH, or both, at Week 48 and treating all cases of withdrawal from treatment for lack of efficacy or toleration as non-responders. All treatment effect contrasts will be obtained through fitting the Bayesian dose-response and/or exposure-response models with a logit transformation, or logistic regression models.

- Estimand 2.4: Using a composite estimand strategy, in participants with biopsy-confirmed NASH and fibrosis, as assessed by the sponsor-identified central pathologist(s), estimate the treatment effect of DGAT2i doses administered alone and coadministration of DGAT2i + ACCi relative to placebo, and coadministration of DGAT2i + ACCi, relative to DGAT2i alone, in terms of the proportion of 'clinical responders', defined as participants achieving centrally adjudicated improvement of ≥2 points on Total NAFLD Activity Score (NAS) at Week 48 and treating all cases of withdrawal from treatment for lack of efficacy or toleration as non-responders. All treatment effect contrasts will be obtained through fitting the Bayesian dose-response and/or exposure-response models with a logit transformation, or logistic regression models.
- Estimand 2.5: Using a hypothetical estimand strategy, in participants with biopsy-confirmed NASH and fibrosis, as assessed by the sponsor-identified central pathologist(s), estimate the treatment effect of DGAT2i doses administered alone and coadministration of DGAT2i + ACCi relative to placebo, and coadministration of DGAT2i + ACCi, relative to DGAT2i alone, in terms of the population level average percentage change from baseline in liver fat (assessed via MRI-PDFF) at Week 48, assuming all participants had remained in the trial and received treatment as planned without withdrawal up to 48 weeks. Endpoint data collected after treatment withdrawal will be censored. All treatment effect contrasts will be obtained through fitting the Bayesian dose-response and/or exposure-response models, or ANCOVA models.

9.1.2. Hypothesis Tests

For this study there are no formal hypothesis tests planned.

9.2. Sample Size Determination

The sample size estimation for this study is driven by the characterization of dose response and treatment effect using a Bayesian E_{max} study design and modelling approach, which will utilize weakly informative priors for model parameters and will provide the ability to make more precise comparisons between treatment arms. The sample size calculation is based on the primary efficacy endpoint, the proportion of participants with improvement in fibrosis without worsening of NASH or NASH resolution without worsening of fibrosis, or both improvement in fibrosis and NASH resolution at Week 48.

The DGAT2i ED₅₀ for the histological-based primary endpoint has been assumed to be slightly higher than the projected EC₅₀ for reduction in liver fat which was estimated from a preliminary population pharmacokinetic model based on previous clinical studies with DGAT2i. Therefore, the DGAT2i ED₅₀ was estimated to be approximately 30 mg BID and the placebo responder rate (E₀) was estimated to be 16%. It is estimated that a total sample size of 350 participants (50 randomized participants per arm) will give acceptable probabilities to make decisions about the dose response in a NASH population based on simulation studies. At the theoretical E_{max} of 0.6 (ie, a 60% responder rate), there would be enough precision to show a greater than 24% difference in the primary endpoint responder rate between placebo and the second highest BID dose of DGAT2i (ie, 150 mg BID) with a probability of at least 89%.

In addition, this sample size will provide adequate precision to assess whether DGAT2i + ACCi provides a higher responder rate than DGAT2i monotherapy with a probability of 82% if the true effect size is at least 6%.

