9.3. Analysis Sets

For purposes of analysis, the following analysis sets are defined:

Patients Analysis Set	Description	
Enrolled	All participants who sign the PreQ ICD	
Randomly assigned to investigational product	All randomized participants	
Evaluable	Defined according to the Full Analysis Set:	
	All randomized participants who take at least 1 dose of investigational product who have provided baseline data for the primary endpoint (i.e. baseline biopsy data). Participants will be analyzed according to the treatment group they are randomized to.	
	 The only exception to this is for participants randomized before Protocol Amendment 1 is enacted who are randomized to either of the 2 QD dosing regimens of DGAT2i alone, who switch to the corresponding BID dosing regimen of DGAT2i alone, and will be analyzed under that treatment group. 	
Safety	All randomized participants who take at least 1 dose of investigational product. Participants will be analyzed according to the treatment they actually received.	
	 The only exception to this is for participants randomized before Protocol Amendment 1 is enacted who are randomized to either of the 2 QD dosing regimens of DGAT2i alone, who switch to the corresponding BID dosing regimen of DGAT2i alone, and will be analyzed under that treatment group. 	

Final Protocol Amendment 1, 30 August 2021

Defined Analysis Data Set (at the data level) – endpoint specific	Description		
All biopsy-derived endpoints			
Biopsy-based Composite Estimand	If a participant discontinues treatment or from the study due to lack of efficacy or toleration prior to Week 48 or if they do not have Week 48 Biopsy data, they will be considered to be a non-responder.		
Biopsy-based Hypothetical Estimand	Any available biopsy data for all participants collected before or at the time of treatment withdrawal will be included in the analysis, even if they have withdrawn from treatment for lack of efficacy or toleration. Endpoint data collected after treatment withdrawal will be censored.		
All MRI-PDFF-derived endpoints (in Imaging Substudy)			
MRI-based Hypothetical Estimand	Any available MRI data for all participants collected before or at the time of treatment withdrawal will be included in the analysis, even if they have withdrawn from treatment for lack of efficacy or toleration. Endpoint data collected after treatment withdrawal will be censored.		

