2.2. Study Design

The detailed set-up of the study is summarized below -

Figure 1. Study Design

This is a multicenter, multinational, randomized, double-blind, double-dummy, placebo-controlled, parallel-group, evaluation of DGAT2i alone, and DGAT2i+ACCi. Approximately 350 participants (50 per arm) with biopsy confirmed NASH with F2-F3 fibrosis, as assessed by sponsor-identified central pathologist(s), will be randomly assigned to the study intervention to ensure approximately 280 evaluable participants (40 per arm) offer evaluable data for the primary objective.

Participants will be randomized in a balanced ratio, using a computer-generated randomization code, to receive either double-blind, double-dummy placebo, 1 of 4 doses/dosing regimens of DGAT2i alone, or 1 of 2 dose-levels of DGAT2i+ACCi for a treatment duration of up to 48-weeks.

For participants randomized before Protocol Amendment 1 is enacted, those randomized to either of the 2 QD (DGAT2i 150 mg QD and DGAT2i 300 mg QD) dosing regimens of DGAT2i alone will remain in the study but will be switched to the corresponding BID dosing regimen of DGAT2i alone, maintaining the assigned total daily dose and the double-blind, double-dummy design. New randomization to the QD treatment arms will cease, after Health Authority (where applicable) and IRB/EC approvals of Protocol Amendment 1. Therefore, following Protocol Amendment 1, participants will be randomized to one of the following treatment arms:

Placebo

DGAT2i (Ervogastat) BID dose arms (for characterization of dose-response):

- DGAT2i 25 mg BID, total daily dose of 50 mg
- DGAT2i 75 mg BID, total daily dose of 150 mg
- DGAT2i 150 mg BID, total daily dose of 300 mg
- DGAT2i 300 mg BID, total daily dose of 600 mg

DGAT2i (Ervogastat) + ACCi (Clesacostat) coadministration dose arms:

- DGAT2i 150 mg BID + ACCi 5 mg BID
- DGAT2i 300 mg BID + ACCi 10 mg BID

The treatment group labels in programmed outputs will be as follows:

Placebo	PF-5571	PF-5571	PF-5571	PF-5571	PF-5571	PF-5571	Tota1
	25 mg	75 mg	150 mg	150 mg	300 mg	300 mg	
	BID	BID	BID	BID+	BID	BID+	
				PF1304 5		PF1304 10	
				mg BID		mg BID	

Following footnote to be included on all tables: PF5571 = Ervogastat and PF1304 = Clesacostat Note: A 'Total' column is required when summarizing baseline of population randomized

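### Section 9.2's 89% does not appear to allow for the smaller treatment difference that results when the expected 20% without evaluable biopsies are counted as non-responders

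*Protocol*

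**What the plan says.** Protocol Section 9.2 plans "a total sample size of 350 participants (50 randomized participants per arm"). It takes three inputs: "the placebo responder rate (E₀) was estimated to be 16"%, a maximum described as "At the theoretical E_{max} of 0.6 (ie, a 60% responder rate"), and "the DGAT2i ED₅₀ was estimated to be approximately 30 mg BID". The target contrast is put as follows: "greater than 24% difference in the primary endpoint responder rate between placebo and the second highest BID dose of DGAT2i (ie, 150 mg BID"). Section 9.2 reports, from simulations that are not shown, that the design reaches this target "with a probability of at least 89"%. The protocol synopsis repeats this result.

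The reason for randomising 350 is given in the protocol synopsis, Protocol Section 4.1 and SAP Section 2.2: "to ensure approximately 280 evaluable participants (40 per arm) offer evaluable data for the primary objective".

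The primary analysis treats missing biopsies differently. The set named Evaluable (Protocol Section 9.3; SAP Section 4, Table 8) is everyone dosed who has a baseline biopsy. For the composite estimand, Protocol Section 9.3 says of participants that "if they do not have Week 48 Biopsy data, they will be considered to be a non-responder". SAP Sections 2.1.1, 5.3 and 6.1.1.1 apply the same rule.

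**The concern.** The word evaluable has two meanings here. In the design text it describes about 280 people with usable primary data. In the analysis set it describes nearly all 350. Raising 40 per arm to 50 is the usual allowance when missing participants drop out of the analysis and only precision is lost. Under the composite rule they do not drop out. The denominator stays near 50 per arm, and every missing biopsy pulls the responder rate down. With equal missingness in all arms, the difference between arms shrinks in the same proportion as the rates.

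The 89% is the only figure offered to justify the sample size for dose response, and Protocol Section 2.1 says the study will inform the Phase 3 doses. A reader should know whether, under the assumed effect, the chance of falling short of 24 points is about 1 in 10 or nearer 1 in 4.

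**Working it through.** **Inputs.** Placebo rate 0.16, maximum rate 0.60, ED50 30 mg BID, threshold 0.24 and 50 per arm (Protocol Section 9.2); 280/350 with evaluable data (SAP Section 2.2), so the missing fraction is 1 − 280/350 = 0.20. Assumptions: 60% is the asymptotic responder rate, and missingness is equal across arms.

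**True rate at 150 mg BID.** The Emax fraction is 150/(150 + 30) = 0.833.
- Logit scale: logit(0.16) = −1.658 and logit(0.60) = 0.405, a distance of 2.064. The rate is expit(−1.658 + 2.064 × 0.833) = 0.515, a difference of 0.355.
- Probability scale: 0.16 + 0.44 × 0.833 = 0.527, a difference of 0.367.

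**The plan's figure, undiluted.** P(observed difference > 0.24) = Φ((difference − 0.24)/SE), with SE = √[(p₀(1 − p₀) + p₁(1 − p₁))/n]. On the logit scale:
- n = 40: SE 0.098, z = (0.355 − 0.24)/0.098 = 1.18, probability 0.88.
- n = 50: SE 0.088, z = 1.32, probability 0.91.

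On the probability scale the values are 0.90 and 0.93. The stated 0.89 is therefore recovered to within two points at 40 per arm on either scale, and at 50 per arm on the logit scale.

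**With 20% scored as non-responders, n = 50.** Both rates are multiplied by 0.80.
- Logit scale: 0.128 against 0.412, difference 0.284, SE 0.084, z = 0.53, probability 0.70.
- Probability scale: 0.128 against 0.421, difference 0.293, probability 0.74.

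**Check under the planned model.** Trials of placebo and the four monotherapy arms were simulated and analysed with the three-parameter Emax model. The priors were those in Protocol Section 9.4.2, with the ED50 prior taken on the log scale. The table is for the logit scale, with the Emax prior centred on 2.06 (the distance from logit 0.16 to logit 0.60).

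| Scenario | Pairwise | Emax: posterior mean > 24 points | Emax: average posterior probability of > 24 points |
|---|---|---|---|
| No dilution, n = 40 | 0.88 | about 0.95 | about 0.87 |
| No dilution, n = 50 | 0.91 | about 0.96 | about 0.89 |
| 10% scored as non-responders, n = 50 | 0.82 | about 0.89 | about 0.81 |
| 20% scored as non-responders, n = 50 | 0.70 | about 0.75 | about 0.70 |

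Across both scales, both Emax criteria and an alternative prior centre of logit(0.60) = 0.41, the 20% row runs from about 0.64 to 0.78. The undiluted posterior-mean criterion runs from 0.92 to 0.97.

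**The case against.** The strongest reply is that 16% and 60% may already be composite rates. Section 9.2 calls them responder rates for the primary endpoint, and Section 9.4.2 centres the priors for the composite analysis on the same values. On that reading nothing falls, and about 0.89 to 0.91 stands at 50 per arm on the logit scale. Multiplying by 0.80 would then count missingness twice. This stands: the documents do not exclude it. It would imply rates among biopsied participants of 0.16/0.80 = 20% and 0.60/0.80 = 75%, which appear nowhere.

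A reader might infer that the 280 target proves the rates refer to biopsied participants. It does not. Estimand 1.2 (Protocol Section 9.1.1; SAP Section 2.1.3) also serves the primary objective and treats missing Week 48 biopsies as missing at random. There, a participant without a biopsy is lost information, and a target of 280 makes sense whatever the rates mean.

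The 89% also cannot be traced to one calculation. The decision rule and the number per arm simulated are not given. Under the planned model with a posterior-mean criterion, the undiluted result is above 0.89, and 10% dilution gives about 0.89. Some dilution could therefore already be in the figure. This too stands, and it is why the point says only that the 89% does not appear to allow for the smaller difference.

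Finally, no formal hypothesis tests are planned (Protocol Section 9.1.2), so the 89% is the probability of exceeding a threshold and not the power of a test. That limits the consequence but does not remove the need for a correct figure.

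**Conclusion.** The point holds in conditional form. The plan expects about 20% without evaluable primary data, its primary analysis counts missing Week 48 biopsies as non-response, and Section 9.2 mentions no reduction in the difference. On the natural reading of inflating 40 per arm to 50, the stated probability is not what the design delivers under its own rules. If the rates apply to biopsied participants and 20% are missing equally in every arm, the probability is about 0.70 to 0.76, with a range of about 0.64 to 0.78 by scale and criterion. At 10% missing it is about 0.80 to 0.90. Participants who have a biopsy but stopped treatment for lack of efficacy or toleration are also scored as non-responders (SAP Section 2.1.1). The 20% does not obviously cover them, so they could add to the dilution.

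Two stronger conclusions are not supported. One is that the 89% is an arithmetic error: it is recovered from the stated inputs. The other is that the true probability is 70 to 76%: that depends on what 16% and 60% mean, which neither document says. Under either meaning, Section 9.2 leaves out something the reader needs.

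**What to change.** Rerun the existing simulation with 50 per arm and the expected 20% scored as non-responders. Restate the resulting probability in Section 9.2 and the synopsis, together with the decision rule and the number per arm simulated. State there whether 16% and 60% are rates among biopsied participants or composite rates.

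If they are already composite, keep the 89%, say so, and state that the target of 280 evaluable does not enter the primary calculation. The 70 to 76% found here should not be written in as the replacement value; the figure should come from the sponsor's own simulation.

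The cost is one rerun and a few sentences. No participants are added and no analysis changes. The stated probability may become less favourable.

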9.3. Analysis Sets

For purposes of analysis, the following analysis sets are defined:

Patients Analysis Set	Description	
Enrolled	All participants who sign the PreQ ICD	
Randomly assigned to investigational product	All randomized participants	
Evaluable	Defined according to the Full Analysis Set:	
	All randomized participants who take at least 1 dose of investigational product who have provided baseline data for the primary endpoint (i.e. baseline biopsy data). Participants will be analyzed according to the treatment group they are randomized to.	
	 The only exception to this is for participants randomized before Protocol Amendment 1 is enacted who are randomized to either of the 2 QD dosing regimens of DGAT2i alone, who switch to the corresponding BID dosing regimen of DGAT2i alone, and will be analyzed under that treatment group. 	
Safety	All randomized participants who take at least 1 dose of investigational product. Participants will be analyzed according to the treatment they actually received.	
	 The only exception to this is for participants randomized before Protocol Amendment 1 is enacted who are randomized to either of the 2 QD dosing regimens of DGAT2i alone, who switch to the corresponding BID dosing regimen of DGAT2i alone, and will be analyzed under that treatment group. 	

Final Protocol Amendment 1, 30 August 2021

Defined Analysis Data Set (at the data level) – endpoint specific	Description		
All biopsy-derived endpoints			
Biopsy-based Composite Estimand	If a participant discontinues treatment or from the study due to lack of efficacy or toleration prior to Week 48 or if they do not have Week 48 Biopsy data, they will be considered to be a non-responder.		
Biopsy-based Hypothetical Estimand	Any available biopsy data for all participants collected before or at the time of treatment withdrawal will be included in the analysis, even if they have withdrawn from treatment for lack of efficacy or toleration. Endpoint data collected after treatment withdrawal will be censored.		
All MRI-PDFF-derived endpoints (in Imaging Substudy)			
MRI-based Hypothetical Estimand	Any available MRI data for all participants collected before or at the time of treatment withdrawal will be included in the analysis, even if they have withdrawn from treatment for lack of efficacy or toleration. Endpoint data collected after treatment withdrawal will be censored.		

